10.9 Appendix 9: New York Heart Association (NYHA) Classification

The stages of heart failure will be assessed according to the NYHA functional classification system. This system relates symptoms to everyday activities and the participant’s quality of life.

Table 10–5: New York Heart Association (NYHA) Classification

Class	Participant symptoms
Class I (mild)	No limitation of physical activity. Ordinary physical activity does not cause undue fatigue, palpitation, or dyspnea (shortness of breath).
Class II (mild)	Slight limitation of physical activity. Comfortable at rest, but ordinary physical activity results in fatigue, palpitation, or dyspnea.
Class III (moderate)	Marked limitation of physical activity. Comfortable at rest, but less than ordinary activity causes fatigue, palpitation, or dyspnea.
Class IV (severe)	Unable to carry out any physical activity without discomfort. Symptoms of cardiac insufficiency at rest. If any physical activity is undertaken, discomfort is increased.

10.10 Appendix 10: CYP3A4 Inhibitors and Inducers**CYP3A4 inducers and inhibitors**

Table 10–6 presents an overview of CYP3A4 inducers and **strong** CYP3A4 inhibitors. CYP3A4 inducers and **strong** CYP3A4 inhibitors are NOT allowed due to drug-drug-interaction with regorafenib.

Table 10–6: An Overview of CYP3A4 Inducers and Strong CYP3A4 Inhibitors

STRONG CYP3A4 Inhibitors	CYP3A4 Inducers
Boceprevir	Avasimibe
Clarithromycin	Bosentan
Cobicistat, only available in the combination with elvitegravir, emtricitabine, tenofovir or disoproxil fumarate	Carbamazepine
Conivaptan	Efavirenz
Delavirdine	Enzalutamide
Idelalisib	Etravirine
Indinavir	Fosphenytoin
Itraconazole	Hypericum perforatum (St John's Wort)
Ketoconazole	Lersivirine
Lopinavir	Lumacaftor
Mibefradil	Methylphenobarbital
Miconazole	Mitotane
Nefazodone	Modafinil
Nelfinavir	Nafcillin
Posaconazole	Phenobarbital
Ritonavir	Phenytoin
Saquinavir	Primidone
Telaprevir	Rifabutin
Telithromycin	Rifampicin
Tipranavir	Rifamycin
Troleandomycin	Semagacestat
Voriconazole	Thioridazine

A STRONG inhibitor is **NOT allowed during this clinical trial**.
CYP3A4 inducers are **NOT allowed during this clinical trial**.

[figure not shown]
The CYP3A4 inducers and strong CYP3A4 inhibitors in Table 10–6 were identified using the Bayer-World Health Organization's Drug Dictionary (WHO-DD) and Bayer drug groupings for CYP3A4 inducers and CYP3A4 inhibitors.

10.11 Appendix 11: Guidance for Management of Immune-Related Adverse Events

The following AE management algorithms apply criteria from NCI-CTCAE v4

GI Adverse Event Management Algorithm

[figure not shown]
Rule out non-inflammatory causes. If non-inflammatory cause is identified, treat accordingly and continue I-O therapy. Opiates/narcotics may mask symptoms of perforation. Infliximab should not be used in cases of perforation or sepsis.

Patients on IV steroids may be switched to an equivalent dose of oral corticosteroids (e.g. prednisone) at start of tapering or earlier, once sustained clinical improvement is observed. Lower bioavailability of oral corticosteroids should be taken into account when switching to the equivalent dose of oral corticosteroids.

Renal Adverse Event Management Algorithm

[figure not shown]
Rule out non-inflammatory causes. If non-inflammatory cause, treat accordingly and continue I-O therapy.

Patients on IV steroids may be switched to an equivalent dose of oral corticosteroids (e.g. prednisone) at start of tapering or earlier, once sustained clinical improvement is observed. Lower bioavailability of oral corticosteroids should be taken into account when switching to the equivalent dose of oral corticosteroids.

Pulmonary Adverse Event Management Algorithm

[figure not shown]
Rule out non-inflammatory causes. If non-inflammatory cause, treat accordingly and continue I-O therapy. Evaluate with imaging and pulmonary consultation.

Patients on IV steroids may be switched to an equivalent dose of oral corticosteroids (e.g. prednisone) at start of tapering or earlier, once sustained clinical improvement is observed. Lower bioavailability of oral corticosteroids should be taken into account when switching to the equivalent dose of oral corticosteroids

Hepatic Adverse Event Management Algorithm

Rule out non-inflammatory causes. If non-inflammatory cause, treat accordingly and continue I-O therapy. Consider imaging for obstruction.

[figure not shown]

Patients on IV steroids may be switched to an equivalent dose of oral corticosteroids (e.g. prednisone) at start of tapering or earlier, once sustained clinical improvement is observed. Lower bioavailability of oral corticosteroids should be taken into account when switching to the equivalent dose of oral corticosteroids.

*The recommended starting dose for grade 4 hepatitis is 2 mg/kg/day methylprednisolone IV.

Endocrinopathy Adverse Event Management Algorithm

[figure not shown]
Rule out non-inflammatory causes. If non-inflammatory cause, treat accordingly and continue I-O therapy. Consider visual field testing, endocrinology consultation, and imaging.

Patients on IV steroids may be switched to an equivalent dose of oral corticosteroids (e.g. prednisone) at start of tapering or earlier, once sustained clinical improvement is observed. Lower bioavailability of oral corticosteroids should be taken into account when switching to the equivalent dose of oral corticosteroids.

Skin Adverse Event Management Algorithm

Rule out non-inflammatory causes. If non-inflammatory cause, treat accordingly and continue I-O therapy.

[figure not shown]
Patients on IV steroids may be switched to an equivalent dose of oral corticosteroids (e.g. prednisone) at start of tapering or earlier, once sustained clinical improvement is observed. Lower bioavailability of oral corticosteroids should be taken into account when switching to the equivalent dose of oral corticosteroids.

*Refer to NCI CTCAE v4 for term-specific grading criteria.

^If SJS/TEN is suspected, withhold I-O therapy and refer patient for specialized care for assessment and treatment. If SJS or TEN is diagnosed, permanently discontinue I-O therapy.

Neurological Adverse Event Management Algorithm

Rule out non-inflammatory causes. If non-inflammatory cause, treat accordingly and continue I-O therapy.

Patients on IV steroids may be switched to an equivalent dose of oral corticosteroids (e.g. prednisone) at start of tapering or earlier, once sustained clinical improvement is observed. Lower bioavailability of oral corticosteroids should be taken into account when switching to the equivalent dose of oral corticosteroids.

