6.6.2 Toxicity Management and Dose Modification Recommendations for Nivolumab

AEs (both non-serious and serious) associated with nivolumab exposure may represent an immunologic etiology. These AEs may occur shortly after the first dose or several months after the last dose of treatment. Therefore, early recognition and initiation of treatment is critical to reduce complications.

There will be no dose reductions for nivolumab. Treatment can be delayed for nivolumab related AEs. If the criteria to resume treatment are met, the subject should restart treatment at the next scheduled time point per protocol.

Nivolumab administration should be delayed for the following:

- Grade 2 non-skin, drug-related AE, with the exception of fatigue
- Grade 2 drug-related creatinine, AST, ALT and/or Total Bilirubin abnormalities
- Grade 3 skin, drug-related AE
- Grade 3 drug-related laboratory abnormality, with the following exceptions:
 - Grade 3 lymphopenia or asymptomatic amylase or lipase does not require dose delay
 - Grade ≥ 3 AST, ALT, Total Bilirubin will require dose discontinuation (see Section 6.6.2.1)
- Any adverse event, laboratory abnormality, or intercurrent illness which, in the judgment of the investigator, warrants delaying the dose of study medication.

There are no recommended dose modifications for hypothyroidism or hyperthyroidism. Interrupt or slow the rate of infusion in participants with mild or moderate (Grade 1-2)

infusion reactions. Discontinue nivolumab in participants with severe or life-threatening infusion reactions (Grade 3-4) (see Section 6.6.2.4).

Participants who require delay of nivolumab should be re-evaluated weekly or more frequently if clinically indicated and resume nivolumab dosing when re-treatment criteria are met (see Section 6.6.2.2). The dose modification can occur independently for the 2 drugs used if toxicity can be clearly attributed to one of the drugs. Resumption of regorafenib dosing is not required to receive further nivolumab dosing and vice versa. Treatment with individual drugs (regorafenib or nivolumab) may continue on schedule even if other drug is interrupted or permanently discontinued due to toxicity.

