6.6.2.1 Nivolumab Treatment – Permanent Discontinuation

- Any Grade 2 drug-related uveitis, eye pain or blurred vision that does not respond to topical therapy and does not improve to Grade 1 severity within the re-treatment period OR requires systemic treatment
- Any Grade 3 non-skin, drug-related AE lasting >7 d or recurs, with the following exceptions for laboratory abnormalities, drug-related uveitis, pneumonitis, bronchospasm, neurologic toxicity, hypersensitivity reactions, infusion reactions, and endocrinopathies:
 - Grade 3 drug-related uveitis, pneumonitis, bronchospasm, neurologic toxicity, myocarditis, hypersensitivity reaction, or infusion reaction of any duration requires discontinuation
 - Grade 3 drug-related endocrinopathies, adequately controlled with only physiologic hormone replacement do not require discontinuation. Adrenal insufficiency requires discontinuation regardless of control with hormone replacement.
 - Grade 3 drug-related laboratory abnormalities do not require treatment discontinuation except:
 - Grade 3 drug-related thrombocytopenia >7 d or associated with bleeding requires discontinuation
 - Grade ≥ 3 drug-related AST, ALT or total Bilirubin requires discontinuation
 - Concurrent AST or ALT > 3 x ULN and total bilirubin > 2x ULN
- In most cases of Grade 3 AST or ALT elevation, nivolumab treatment will be permanently discontinued. If the investigator determines a possible favorable benefit/risk ratio that warrants continuation of nivolumab treatment, a discussion between the investigator and the Sponsor must occur.
- Any Grade 4 drug-related adverse event or laboratory abnormality (including but not limited to creatinine, AST, ALT, or Total Bilirubin), except for the following events which do not require discontinuation:
 - Grade 4 neutropenia ≤ 7 d
 - Grade 4 lymphopenia or leukopenia or asymptomatic amylase or lipase
 - Isolated Grade 4 electrolyte imbalances/abnormalities that are not associated with clinical sequelae and are corrected with supplementation/appropriate management within 72 hr of their onset

- Grade 4 drug-related endocrinopathy adverse events, such as, hyper- or hypothyroidism, or glucose intolerance, which resolve or are adequately controlled with physiologic hormone replacement (corticosteroids, thyroid hormones) or glucose-controlling agents, respectively, may not require discontinuation after discussion with and approval from the Sponsor.

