6.6.2.2 Criteria to Resume Nivolumab Treatment

Participants may resume treatment with nivolumab when the drug-related AE(s) resolve to Grade \leq 1 or baseline value, with the following exceptions:

Participants may resume treatment in the presence of Grade 2 fatigue

Participants who have not experienced a Grade 3 drug-related skin AE may resume treatment in the presence of Grade 2 skin toxicity

For participants with Grade 2 AST, ALT and/or Total Bilirubin Abnormalities, dosing may resume when laboratory values return to baseline and management with corticosteroids, if needed, is complete.

Drug-related pulmonary toxicity, diarrhea or colitis must have resolved to baseline before treatment is resumed. Participants with persistent Grade 1 pneumonitis after completion of a steroid taper over at least 1 month may be eligible for retreatment if discussed with and approved by Sponsor.

Participants with drug-related endocrinopathies adequately controlled with only physiologic hormone replacement may resume treatment after consultation with the Sponsor. Adrenal insufficiency requires discontinuation regardless of control with hormone replacement.

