6.6.2.3 Management of Immune-Mediated AEs

Because of the potential for clinically meaningful nivolumab related AEs requiring early recognition and prompt intervention, management algorithms have been developed for suspected pulmonary toxicity, GI toxicity, hepatotoxicity, endocrinopathy, skin toxicity, neurological toxicity, and renal toxicity. These adverse event management algorithms are included in Section 10.11.

These general guidelines constitute guidance to the Investigator and may be supplemented by discussions with the Sponsor. A general principle is that differential diagnoses should be

diligently evaluated according to standard medical practice. Non-inflammatory etiologies should be considered and appropriately treated. Corticosteroids are a primary therapy for immune related adverse events. The oral equivalent of the recommended IV doses may be considered for ambulatory patients with low-grade toxicity. The lower bioavailability of oral corticosteroids should be taken into account when switching to the equivalent dose of oral corticosteroids. Consultation with a medical or surgical specialist, especially prior to an invasive diagnostic or therapeutic procedure, is recommended.

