 - Unacceptable toxicity, i.e. event requiring permanent discontinuation of nivolumab according to dose modification guidance in Section 6.6.2.1.

Withdrawal from active FU

Participants *must* be withdrawn from active FU if any of the following occurs:

- At their own request or at the request of their legally acceptable representative. At any time during the study and without giving reasons, a participant may decline to participate further. The participant will not suffer any disadvantage as a result.
- Radiologically confirmed PD is observed and/or clinical progression occurs (provided safety visits have been performed)
- Start of subsequent systemic anti-cancer treatment (provided safety visits have been performed)
- Development of a second primary malignancy that requires a different treatment
- Substantial non-compliance with the requirements of the study
- Withdrawal of consent to active FU visits

- If, in the investigator's opinion, continuation of the active FU visits would be harmful to the participant's well-being
- Participants lost to FU
- Death

Withdrawal from long-term FU

Participants *must* be withdrawn from long-term FU if any of the following occurs:

- Withdrawal of consent to long-term FU
- Participants lost to FU
- Death

Participants **MAY** be withdrawn from the study treatment combination for the following reasons:

- At the specific request of the sponsor and in liaison with the investigator (e.g., obvious non-compliance, safety concerns).
- Withdrawal of nivolumab only: discontinuation of nivolumab may be considered for participants who have attained a confirmed complete response (CR), that have been received at least 8 infusions (32 weeks) of nivolumab and had at least 2 infusions with nivolumab beyond the date when the initial CR was declared.

Discontinuation of study intervention for abnormal liver function should be considered by the Investigator when a participant meets one of the conditions outlined in [Table 6–6](#) or if the Investigator believes that it is in best interest of the participant.

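### Diagnosed SJS or TEN recorded as a Grade 3 skin event gets two different nivolumab instructions: Appendix 11 stops the drug for good, while 6.6.2 to 6.6.2.2 delay it and let it restart

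*Protocol*

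**What the plan says.** Protocol 10.11 (Appendix 11), in a footnote to the skin algorithm, sets two steps by diagnosis. On suspicion: "If SJS/TEN is suspected, withhold I-O therapy and refer patient for specialized care for assessment and treatment". On diagnosis: "If SJS or TEN is diagnosed, permanently discontinue I-O therapy".

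The dose-modification text is organised by grade:

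- **6.6.2** lists "Grade 3 skin, drug-related AE" among the events that delay nivolumab. It adds that a participant who meets the resumption criteria should restart at the next scheduled time point. A further item allows delay for any event on the investigator's judgement.
- **6.6.2.1** (permanent discontinuation) includes "Any Grade 3 non-skin, drug-related AE lasting >7 d or recurs" and, separately, "Any Grade 4 drug-related adverse event or laboratory abnormality". It ends with an investigator-judgement item for substantial clinical risk. SJS and TEN are not named.
- **6.6.2.2** allows resumption at Grade 1 or lower, or at baseline, with listed exceptions. The one for skin is "Participants who have not experienced a Grade 3 drug-related skin AE may resume treatment in the presence of Grade 2 skin toxicity".
- **6.6.2.3** sends the reader to 10.11 for the algorithms, skin toxicity included, and says "These general guidelines constitute guidance to the Investigator".
- **7.1** requires nivolumab to be withdrawn for unacceptable toxicity, described as an "event requiring permanent discontinuation of nivolumab according to dose modification guidance in Section 6.6.2.1". The same section also requires withdrawal if the investigator thinks continuing would be harmful, and for severe allergic reactions, with examples.

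**The concern.** A stopping rule tied to a diagnosis appears only in an appendix footnote. The list of permanent stops that 7.1 cites for nivolumab toxicity does not carry it. That list limits its Grade 3 rule to non-skin events, so a Grade 3 skin event falls under delay and restart instead.

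Two things are at stake. The first is participant safety: a site applying 6.6.2 to 6.6.2.2 could restart nivolumab in someone whom the protocol's own appendix would take off it permanently. The second is consistent recording. Protocol 8.3 records a delayed drug and a withdrawn drug as different actions, and SAP 6.5.2 and 6.5.3 tabulate AEs and SAEs that led to withdrawal. The same event could be counted differently depending on which text a site followed.

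**Working it through.** The documents state no figure on this point and no formula applies. The check sets the rules side by side, by stage and grade. The documents do not grade SJS or TEN, so the grade in each case is an assumption.

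1. **Suspected, Grade 3.** 6.6.2 delays and Appendix 11 withholds. These agree.
2. **Suspected, below Grade 3.** Appendix 11 withholds. 6.6.2 has no skin-specific delay at this grade, but its investigator-judgement item permits one. A site can comply with both.
3. **Diagnosed, Grade 4.** 6.6.2.1 stops nivolumab for any Grade 4 drug-related event, and no skin event is among its exceptions. Appendix 11 also stops it. These agree.
4. **Diagnosed, Grade 3.**
   - Appendix 11: permanent discontinuation.
   - 6.6.2: delay, then the participant should restart when the criteria are met.
   - 6.6.2.1: the Grade 3 stop does not apply, because it covers non-skin events only, and no other item names the event.
   - 6.6.2.2: after a Grade 3 skin event, resuming at Grade 2 skin toxicity is not allowed, but resuming at Grade 1 or lower, or baseline, is. There is no SJS/TEN exception.
   - 7.1: the nivolumab toxicity item refers to 6.6.2.1, which does not list the event.

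   These disagree.

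The silence on SJS/TEN is not because the dose rules avoid diagnoses. 6.6.2.1 names uveitis, pneumonitis, myocarditis and others, and 6.6.2.2 repeats the stop for adrenal insufficiency regardless of hormone control. A reader could reasonably take an unnamed diagnosis to follow the general grade rule.

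On precedence, 6.6.2.3 points to Appendix 11 and calls its content guidance. But 7.1 also describes 6.6.2.1 as guidance, and 6.6.2 is headed as recommendations. The labels do not rank one text above the other, and no section does so expressly.

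On size, the documents give no SJS/TEN rate, so an expected number of cases cannot be derived. With 70 treated participants, one case recorded differently moves a table entry by 1/70 = 1.4%.

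**The case against.** The strongest reply is that the protocol already leads a careful site to stop. Section 6.6.2.3 refers to Appendix 11 for skin toxicity, so the specific rule can be read as supplementing the general one. Section 6.6.2.1 has a substantial-risk item. Section 7.1 requires withdrawal when continuing would be harmful and for severe allergic reactions; that list is open-ended and includes a severe skin reaction. Serious events reach the sponsor within 24 hours (8.3.1), so the absence of a DMC (9.6) would not leave a case unseen.

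Much of this stands, and it makes an actual restart less likely. It does not remove the contradiction. The judgement items are discretionary, whereas the footnote is unconditional. The allergic-reaction item does not name SJS or TEN, so a site would have to infer that it applies. The cross-reference does not say which text prevails.

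A second reply is that no text requires re-treatment, because 6.6.2.2 only permits it. That overlooks 6.6.2, which says the participant should restart once the criteria are met.

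A reader might also infer three stronger points, which the documents do not support:

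- **That the rules also clash at suspicion.** Cases 1 and 2 of the working show that they do not.
- **That the dose-modification sections can only ever delay a skin event.** 6.6.2.1 stops nivolumab at Grade 4 and on substantial risk.
- **That a probability can be put on the problem.** Any such figure needs an assumed SJS/TEN rate. It would also count every case, not only those diagnosed, recorded as Grade 3 and then restarted.

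**Conclusion.** The point holds in a narrow form. For SJS or TEN that is diagnosed and recorded as a Grade 3 drug-related skin event, Appendix 11 and 6.6.2 to 6.6.2.2 give different instructions on restarting nivolumab, and no section resolves the difference.

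This rests on two assumptions. One is that such a case can be recorded as Grade 3; the documents neither say so nor rule it out. The other is that the footnote applies whatever the grade. Its wording sets no grade condition, but the algorithm figure it belongs to is not shown in the text reviewed, so where its marker sits could not be checked.

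The statistical effect is small: safety is analysed without formal tests (SAP 6.5), and one case would move a descriptive count by one. The point matters because it concerns possible re-exposure, and because it is easy to correct. Nothing here implies that either clinical rule is the right one.

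**What to change.** Reconcile Protocol 6.6.2, 6.6.2.1, 6.6.2.2 and the nivolumab toxicity item in 7.1 with the Appendix 11 skin footnote, so that a single instruction covers diagnosed SJS/TEN. Name the event in the section that 7.1 cites. Add one sentence stating which text prevails where 6.6.2 and Appendix 11 differ. The sponsor's clinical team should choose the rule.

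The cost is a few lines in a protocol amendment or a clarification letter to sites. No new data, procedures or analyses are needed.

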10.12 Appendix 12: Abbreviations

Table 10–7: Abbreviations

5-FU	5-fluorouracil
ADA	Anti-drug-antibodies
AE	Adverse event
AJCC	American Joint Committee on Cancer
ALT	Alanine aminotransferase
ALP	Alkanine phosphatase
Ang1	Angiopoietin 1
aPTT	Activated partial thromboplastin time
AST	Aspartate aminotransferase
AUC	Area under the plasma concentration time curve
BCRP	Breast cancer resistance protein
BICR	Blinded independent central review
BP	Blood pressure
BRAF	Proto-oncogen BRAF
BUN	Blood urea nitrogen
BTLA	B- and T-lymphocyte attenuator
C	Cycle
CCL	cc-chemokine ligand
CD	Cluster of differentiation

CEA	Carcinoembryonic antigen
CI	Confidence interval
C _{max}	maximum observed drug concentration
CMS	Consensus molecular subtypes
CMV	Cytomegalovirus
CNS	Central nervous system
CR	Complete response
c-RAF	Proto-oncogen c-RAF
CRC	Colorectal cancer
CSF1R	Colony stimulating factor 1 receptor
CT	Computed tomography
CTCAE	Common terminology criteria for adverse events
ctDNA	Circulating tumor DNA
CTLA-4	Cytotoxic T-lymphocyte-associated protein 4
CYP	Cytochrome P450 (derivates)
D / (d)	Day(s)
DCR	Disease control rate
DICOM	Digital imaging and communication in medicine
DLT	Dose limiting toxicity
DMC	Data monitoring committee
dMMR	Mismatch repair deficient
DOR	Duration of response
EC ₅₀	Half maximal effective concentration
ECG	Electrocardiogram
ECOG	Eastern Cooperative Oncology Group
eCRF	Electronic case report form
EGFR	Epidermal growth factor receptor
EU	European Union
FAS	Full analyses set
FDA	Food and Drug Administration
FSH	Follicle stimulating hormone
FU	Follow-up
GC	Gastric cancer
GCP	Good clinical practice
GIST	Gastrointestinal stroma tumor
HCC	Hepatocellular carcinoma
HCV	Hepatitis C virus
HFSR	Hand foot skin reaction
HIV	Human immunodeficiency virus
HNSCC	Head and neck squamous-cell carcinoma
HR	Hazard ratio
HRT	Hormonal replacement therapy
IB	Investigators brochure
IC ₅₀	Half maximal inhibitory concentration
ICF	Informed consent form
ICH	International Conference on Harmonization
ICOS	Inducible T-cell co-stimulator
iCPD	Confirmed radiographic progression by iRECIST
IEC	Independent Ethics Committees
IFN- γ	Interferon-gamma

IgG	Immunoglobulin
IL	Interleukin
IMAE	Immune-mediated adverse event
INR	International normalized ratio
IRB	Institutional Review Board
iRECIST	Response evaluation criteria in solid tumors for trials testing immunotherapeutics
iUPD	Unconfirmed progressive disease by iRECIST
i.v.	Intravenous
IxRS	Interactive voice/web response system
LPLV	Last patient last visit
M-2	N-oxide
M-5	N-oxide plus N-desmethyl
mCRC	Metastatic colorectal cancer
pMMR	Mismatch repair-proficient
MRI	Magnetic resonance imaging
MSI	Microsatellite instable
MSS	Microsatellite stable
NCI	National Cancer Institute
NSCLC	Non-small cell lung cancer
NYHA	New York Heart Association
ORR	Overall response rate
OS	Overall survival
PCR	Polymerase chain reaction
PD	Progressive disease
PD-1	Programmed cell death protein 1
PD-L1	Programmed cell death protein 1 ligand 1
PET	Positron-emission tomography
PFS	Progression free survival
PID	Participant identification number
PK	Pharmacokinetics
PPK	Population pharmacokinetics
PR	Partial response
PS	Performance status
q.d.	Quaque die (once daily)
RANKL	receptor activator of nuclear factor kappa-B ligand
RAS	rat sarcoma viral oncogene homolog
RCC	Renal cell cancer
RECIST	Response evaluation criteria in solid tumors
RET	Rearranged during transfection
r-PKS	Regorafenib PK analysis set
SAE	Serious adverse event
SAP	Statistical analysis plan
SD	Stable disease
TIL	Tumor infiltrating lymphocytes
TMB	Tumor mutational burden
UGT	UDP-glucuronosyltransferase (derivates)
ULN	Upper limit of normal
UPD	Unconfirmed progressive disease
US	United States

VEGFR	Vascular endothelial growth factor receptor
WOCBP	Woman of childbearing potential

CCI

CCI

CCI

CCI

12. Protocol Amendments

